specialty care when compared to those receiving TAU only. In addition, we anticipate showing that self-directed technology can overcome traditional barriers to implementing person-delivered BAIs in HCV clinics, thereby increasing Veterans' access to these services within medical settings which is a major objective of OMHS, the VA Office of Mental Health Operations (10N), and VA Office of Public Health.

The Office of Mental Health Operation, OMHS, and the VA Office of Public Health consider this intervention affordable and scalable because of its modular and self-directed nature, and are interested in rolling it out across VA if it proves effective. Our findings will support OMHS and Mental Health Operations (10NC) in implementing the Mental Health Uniform Benefits Package by identifying an effective, low-cost intervention for treating alcohol misuse in HCV clinics. This study will also help optimize the implementation and sustained adoption of this intervention by providing our partners with (a) evidence-based recommendations for optimizing the adoption of the web-based BAI within this clinic setting, and (b) a budget impact analysis which will provide an estimate of the short-term budget implications of implementing this technology into HCV clinics nationwide. This study may also provide an alternative, evidence-based approach to treating alcohol misuse in other VA medical settings such as primary care and surgery. Furthermore, OMHS and Mental Health Operations (10NC) is interested in improving access to these services by pushing this technology to Veterans who are not yet in care and those in more rural settings. Finally, our partners find this study valuable because it enhances the link between the Office of Mental Health Services and Office of Public Health.

Population Rationale

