Specifically, we hypothesize that compared to patients in treatment-as-usual (TAU), participants in the web-based BAI plus TAU condition will demonstrate- **H1**: greater reductions in the number of drinking days, average drinks per drinking day, and percentage of heavy drinking days; **H2**: greater improvements in health status, psychological distress, knowledge about liver disease and alcohol use, antiviral treatment eligibility, satisfaction and perceived effectiveness with treatment; and **H3**: increased utilization of VA and non-VA outpatient SUD care at three- and six-months post-treatment.

In addition, we anticipate showing that self-directed technology can overcome traditional barriers to implementing person-delivered BAIs in liver clinics, thereby increasing Veterans' access to these services within medical settings which is a major objective of OMHS, the VA Office of Mental Health Operations (10N), and VA Office of Public Health.

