(c) Patient satisfaction. We will use a brief patient survey that we developed from our preliminary work to assess patients' satisfaction with both treatment conditions. This survey will ask patients to respond to a series of statements regarding their satisfaction with the interventions received (e.g., "I felt comfortable disclosing my alcohol use to a computer program"; "My provider helped me understand how alcohol use may worsen liver disorder(s)."). This assessment will be completed by patients upon completion of the baseline assessment (and upon completion of the web-based BAI for patients assigned to the experimental condition).

Primary Outcomes.

(d) Alcohol quantity and frequency. Reduction in alcohol use will be measured using the 30-day Time Line Follow-Back instrument (TLFB; Sobell & Sobell, 1992). The TLFB is a calendar that provides visual cues to aid persons in retrospective recall of drinking behavior. It uses "cues" (e.g., holidays, birthdays) to help a participant recall drinking behavior (e.g., frequency and quantity of alcohol use) and has been shown to be reliable and accurate when administered individually over the telephone (Sobell et al., 1996). Based on recommendations from the alcohol treatment literature we will assess the *(a) number of drinking days, (b) mean number of drinks per drinking day, and (c) percentage of heavy drinking days* in the prior 30 days as our primary outcomes (Dieperink et al., 2010; Gastfriend et al., 2007). These outcomes will be measured by comparing TLFB drinking data at baseline (30-days prior) to data collected at three- and six-month follow-up (30 days prior).

Secondary Outcomes.

(e) Consequences of alcohol use. The Short Index of Problems (SIP-3months) is a brief, 15-item version of the Drinker Inventory of Consequences (DrInC) which assesses alcohol-related problems over the prior 3-months (Woolard et al., 2004). The SIP has sound psychometric properties (Kenna et al., 2005).

(f) Symptoms of psychological distress. Symptoms of psychological distress will be measured using the Brief Symptoms Inventory (BSI). The BSI instrument provides an overview of a patient's symptoms and their intensity at a specific point in time (Derogatis & Melisaratos, 1983). The reliability, validity, and clinical utility of the BSI instrument are well-established.

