After the interviews and transcriptions are complete, the study coordinator and [name] will begin developing two separate codebooks for patient and providers. Codebook development will be an iterative process. Codebooks will be initially developed based on close readings of 30% of patient (n = 9) and 40% (n = 4) of provider transcripts. Themes that emerge from the patient and provider interviews will be continuously integrated into their respective codebooks. We anticipate that the final set of themes will consist of both themes defined a priori and new themes that emerge from each set of interviews. Upon completion of the initial version of the codebooks, the study coordinator and [name] will discuss the application of the codebooks to each set of interviews. This process will involve practicing applying the codebooks to a single patient and provider interview. When agreement is reached, the study coordinator and [name] will code a random sample of 20% of patient (n = 6) and 20% of provider (n =2) interviews to establish inter rater reliability. Once reliability is established (80% agreement), we will proceed to code the remaining portion of the patient and provider transcripts. Throughout the coding process, the PI and [name] will regularly discuss emerging themes, changing conceptualizations of existing themes, and to prevent drift. They will also consult intermittently with the other Co-Is and consultants to discuss emerging themes and conceptualizations. After data coding is complete, data analysis will begin, focusing on the frequency of code occurrence (by participant and code) and patterns of code co-occurrence for each set of interviews.

Aim 2

Based on findings from prior studies of web-based BAIs with similar follow-up time

frames, we expect an average effect size of .35 to .40 (range is .15 to .67) on alcohol consumption outcomes in response to the web-based BAI (Kypri et al., 2004; Kypri et al., 2008; Neighbors et al., 2004). Assuming a power of 80% of detecting an effect size of .35, an alpha level of .05, a 2-tailed test, a correlation of .5 between repeated measures of an outcome variable, and a 20% attrition rate at 6 months, we estimate that we will need 170 individuals per condition at baseline for a total sample of 340 across both sites, with one half in the experimental condition and TAU condition at each site (i.e., n=85 per condition at Palo Alto, n=85 per condition at San Francisco).

Data Analysis

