Prior to any regression modeling, we will first examine the sample distributions of each outcome variable and predictor variable to help us identify any possible errors in the data (e.g. coding errors). One of the benefits of our proposed use of generalized linear mixed model (GLMM) regression analyses is that it can accommodate a variety of conditional distributions for each outcome variable. Given that we will randomly assign participants to each condition, we expect the two groups to be comparable on baseline demographics and outcome variables at baseline. Nevertheless, we will conduct independent groups t-tests or chi-square analyses to check for any differences between the two groups on demographic characteristics and baseline outcome assessments. If differences are found between groups on any variables, we will control for those variables in subsequent analyses. Next, we will use generalized linear mixed-model (GLMM) regression analyses to compare the two conditions on our primary and secondary outcomes (Raudenbush et al., 2001; Singer et al., 2003). The primary hypothesis is that the slope of drinking outcomes over 0 to 6 months for participants in the web-based BAI plus TAU condition will differ from the TAU only condition. We will use the repeated measures data to fit a model consisting of fixed-effect terms for time since randomization, the time by condition interaction, and the site main effect. Random intercepts will be included to account for possible correlation among repeated measurements due to patient-specific latent factors. We will examine further constraints on the covariance structure and choose the final model by assessing goodness-of-fit. We will also examine the distribution of the outcome variables and associated random error components, choose appropriate link and variance functions (McCullagh & Nelder, 1991), and review any outliers.

Examining Mediators and Moderators

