Prior studies show that the effectiveness of web-based BAIs is at least partly due to the correction of misperceptions about normative alcohol use (i.e., social norms; Borsari & Carey, 2001; Neighbors et al., 2004). Therefore, we will test whether changes in social norms (e.g., descriptive and injunctive norms) mediate the effect of the web-based BAI on alcohol consumption. Following the recommendation of Baron and Kenny (1986), we will conduct a series of analytic steps (using regression models) to determine mediation: (a) we will test the effect of both intervention conditions on alcohol consumption; (b) the effect of intervention conditions on social norms; (c) the effect of social norms on alcohol consumption controlling for intervention condition; and (d) the effect of intervention condition on alcohol consumption after controlling for social norms. In addition, we will examine potential moderators (e.g., severity of alcohol use, coping, psychological distress) that may impact the effectiveness of intervention condition on treatment outcome. This analysis will help us determine whether the effectiveness of the intervention(s) is impacted by these variables at baseline and over the course of each follow-up.

Missing Data Prevention, Detection, and Adjustment

We will make every effort to prevent missing data at each assessment by achieving as high a response rate as possible. Baseline data will be collected during an in-person interview and follow-up assessments will be conducted as telephone interviews by study site

coordinators who have been trained to cover all questions and obtain as complete data as possible while respecting the patient's right to not answer specific questions. Based on previous follow-up studies of SUD patients conducted at our Center, we do not expect rates of missing data on any one variable to be greater than 5% at each assessment over and above missing data due to attrition, nor do we expect missing data to be systematically related to certain outcome variables. Nevertheless, given our plan to use an intent-to-treat approach that includes all patients who are randomized in our GLMM regression models, we will use multiple imputation. Multiple imputation procedure yields more efficient, accurate, and reliable inferences than ad-hoc methods of handling missing data (such as list wise deletion or mean substitution) (Shafer, 1997 Shafer et al., 2002; Little & Rubin, 2002).

Formative Evaluation Data Analysis

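### H1 has three unranked primary outcomes, one alpha and one power figure, and no success rule, so either the .05 or (on the plan's own sizing basis) the 80% does not describe H1

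*Combined protocol and SAP*

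**What the plan says.** - **Section 3.0, Hypotheses.** H1 is that the BAI arm will show "greater reductions in the number of drinking days, average drinks per drinking day, and percentage of heavy drinking days". The three measures are joined by 'and', and no decision rule is attached. H2, in the same sentence, is a longer list joined in the same way.
- **Section 5.5, Primary Outcomes.** The same three measures, all from the 30-day Time Line Follow-Back (TLFB), are assessed "in the prior 30 days as our primary outcomes". None is ranked above the others.
- **Section 5.6, Aim 2 sample size.** "Assuming a power of 80% of detecting an effect size of .35, an alpha level of .05, a 2-tailed test", with "a correlation of .5 between repeated measures of an outcome variable" and 20% attrition at 6 months, leads to 170 per condition. The outcome is not named, and alpha is not divided.
- **Section 5.6, Data Analysis.** "The primary hypothesis is that the slope of drinking outcomes over 0 to 6 months" will differ between conditions. 'Outcomes' is plural and none is singled out. The model is listed as "fixed-effect terms for time since randomization, the time by condition interaction, and the site main effect".
- **Section 5.6, Missing Data.** Beyond attrition, "we do not expect rates of missing data on any one variable to be greater than 5% at each assessment over and above" attrition losses. Multiple imputation is planned.
- **Section 2.0, Significance.** The partner offices "are interested in rolling it out across VA if it proves effective".

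The available text gives no testing order, no multiplicity adjustment, no rule for when H1 is met, and no correlation between the three outcomes.

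**The concern.** H1 is the effectiveness claim, and the partner offices tie their interest in roll-out to it. Three tests will be run, and the plan does not say how they combine into one conclusion. Two rules are possible, and each leaves one of the plan's stated figures not describing H1:

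- **Any one is enough.** The .05 is then the error of each test, not of the claim.
- **All three are required.** The 80% is then the power of each test, not of the claim.

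With no rule written down, the choice could be made after the three results are known without departing from the plan. Other safeguards are limited. Section 5.1 describes a trial in which participants and project staff know the assignment. Section 4.0 has the investigators analyse the data. Section 5.6 leaves the covariance structure and the link and variance functions to be chosen after looking at the data.

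**Working it through.** **1. The plan's own figure.** Inputs from section 5.6: standardised effect .35, two-sided alpha .05, power 80%, repeated-measures correlation .5, attrition 20%.

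- n per arm = 2 × ((1.960 + .842)/.35)² = 128.1 (unrounded z values), so 129. A change score at correlation .5 has variance 2(1 − .5) = 1 and needs the same n.
- Allowing for attrition: 129/.80 = 161.3, so 162, which is slightly below the planned 170.
- Adding the 5% item-missing allowance: 129/(.80 × .95) = 169.7, so 170. The sample size paragraph does not list that allowance.
- Completers: 170 × .80 = 136 per arm. If the 5% were lost as well, 136 × .95 = 129.2. The 129 is a bound, because imputation is planned.

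The 170 is therefore a one-outcome calculation with a small margin.

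**2. Power per outcome.** The mean z is .35 × √(n/2).

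- n = 136: 2.886, and Φ(2.886 − 1.960) = 82.3% (t-test 82.0%).
- n = 129: 2.811, giving 80.3% (t-test 80.0%).

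**3. Assumption needed.** The correlation r between the three outcomes is not given; the stated .5 is between repeated measures of one outcome. I take equal pairwise r from 0 to .9. The upper part is more plausible, because all three measures come from one 30-day TLFB.

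**4. Any one at unadjusted .05, no true effect.**

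- False claim favouring the BAI = 1 − ∫ Φ((1.960 − √r·u)/√(1 − r))³ φ(u) du. At r = 0 this is 1 − .975³ = 7.3%.
- Two-sided error uses the same integral with both tails. At r = 0 it is 1 − .95³ = 14.3%.

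**5. All three required, effect .35 on each.** With μ the mean z from step 2, power = ∫ Φ((μ − 1.960 + √r·u)/√(1 − r))³ φ(u) du. At r = 0 this is .823³ = 55.7% for n = 136 and .803³ = 51.7% for n = 129.

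| r | Any one: favouring BAI (nominal 2.5%) | Any one: two-sided (nominal 5%) | All three: power, n = 136 | All three: power, n = 129 |
|---|---|---|---|---|
| 0 | 7.3% | 14.3% | 55.7% | 51.7% |
| .3 | 6.8% | 13.6% | 60.9% | 57.4% |
| .5 | 6.3% | 12.5% | 64.7% | 61.5% |
| .7 | 5.5% | 10.9% | 69.1% | 66.2% |
| .8 | 4.9% | 9.8% | 71.7% | 69.0% |
| .9 | 4.2% | 8.4% | 75.0% | 72.5% |

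Under the all-three rule, a false claim favouring the BAI requires every null outcome to reach significance, so its probability is at most 2.5%.

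**6. How far the power shortfall depends on the basis.**

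- *Effect .40* (upper end of the plan's expected average), n = 136: mean z = .40 × √68 = 3.298, per-outcome power 91.0%, all-three power 75.3% (r = 0), 80.0% (.5), 86.3% (.9).
- *Slope model exactly as listed, with no condition main effect.* Generalised least squares, visits at 0, 3 and 6 months, compound symmetry .5, a linear effect reaching .35 at month 6, complete data. Mean z is 3.384 at n = 136 (92.3% per outcome; all three 78.6% to 88.2%) and 3.296 at n = 129 (90.9%; 75.2% to 86.3%).
- *Same model with a condition main effect.* Mean z returns to 2.886 and 2.811, so the figures of step 5 apply.

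The any-one error in step 4 does not change with any of these choices.

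**The case against.** The strongest reply is that H1 joins its three measures with 'and', so the natural reading requires all three, and under that reading error is not inflated. The second half is correct. The first half is an inference: H1 states an expectation, and H2 is a list of the same form that nobody would take as needing success on every item. If the sponsor does intend all three, the plan should say so, and the 80% should no longer be presented as if it covered H1.

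A second reply is that the low power figures rest on one basis. This stands in part. At effect .40, or with the mixed model fitted as listed, all-three power reaches or passes 80% over much of the correlation range. The second of these needs the condition main effect left out and complete data. Effects smaller than .35, or unequal across outcomes, would move power the other way.

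A third reply also stands. H1 is directional, so the relevant false-claim rate is 7.3% to 4.2% against 2.5%, rather than the two-sided 14.3% to 8.4%, and the zero-correlation end is the least plausible.

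Two stronger readings are tempting, and the documents do not support either:

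- **That the trial is too small.** The 170 per arm gives 80% to 82% for one outcome on the plan's own inputs, which is what it was sized for.
- **That the planned analysis inflates error.** It does so only if the any-one rule is adopted, and no passage adopts it.

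A reader might also quote 52% to 75% as the effect of correlation alone. That joins the low end at 129 per arm to the high end at 136, and so changes two inputs at once.

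**Conclusion.** The concern holds in this form: three unranked primary outcomes, one alpha, one power figure for an unnamed outcome, and no rule for when H1 is met.

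- **Any-one rule at unadjusted .05:** a false claim favouring the BAI has probability 7.3% to 4.2%, which is 2.9 to 1.7 times the nominal 2.5%.
- **All-three rule:** error is controlled, but at effect .35 and 136 completers per arm the power for H1 is about 56% to 75%, not 80%. It is 52% to 72% at 129 per arm, and only if the 5% item-missing data are also lost.

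The error figures rest on the assumed correlation of 0 to .9 and equicorrelated normal test statistics. The power figures also assume the same effect on every outcome. They are conditional: about 75% to 86% at effect .40 with 136 per arm, and about 75% to 88% across 129 and 136 per arm if the model is fitted as listed, with no condition main effect and complete data. The missing rule does not depend on any of these assumptions, and it should be supplied before outcome data are seen.

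**What to change.** **Recommended.** Before outcome data are seen, state in sections 3.0 and 5.6:

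1. Which one of the three is the single primary outcome, tested at two-sided .05.
2. That H1 is met if and only if that outcome is significant in favour of the BAI.
3. That the other two are tested in a stated fixed sequence at .05, each only if the previous one is significant.
4. That the alpha and power in the sample size paragraph refer to the primary outcome (80% to 82% by two-sample t-test at 129 to 136 per arm).
5. Whether the mixed model contains a condition main effect, with the power of the slope test confirmed for that model.

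The sponsor chooses the order. One consideration is that drinks per drinking day has no value for a participant with no drinking days in the window. Number of drinking days does, and so does percentage of heavy drinking days if its denominator is all 30 days.

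**Acceptable alternatives.**

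- *Holm across the three*, with H1 met if at least one is significant in favour of the BAI. At-least-one power is about 76% to 97% over both sample sizes (r = .9 to 0) if all three effects are .35, but about 66% to 69% if only one is.
- *All three required*, each at .05, with power for H1 restated as about 56% to 75% on the sizing basis (effect .35, 136 per arm).

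**Cost.** Wording only, with no extra participants. Under the fixed sequence, a later outcome cannot be claimed if an earlier one fails, so a real effect confined to the second or third outcome would almost never be claimed (at most 2.5%). Under Holm, power for any one named outcome is about 72% to 78% when all three effects are .35. Under the all-three rule, the stated power for H1 falls below 80% on the sizing basis.

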4.0 Resources and Personnel

This four year study will be based at two sites - the (a) VA Palo Alto Health Care System, VA HSR&D Center for Health Care Evaluation and Liver Clinic, and (b) San Francisco VA Medical Center, Liver Clinic. This study will also collaborate with the VA Women's Health Practice-Based Research Network to provide technical expertise relevant to

administrative functions (e.g., Central IRB) and enhance our team's ability to oversample for women and optimize retention of women participants in our study.

The PI, VAPAHCS and SFVAMC Co-I's, and study coordinators from each site will have access to protected health information. De-identified information will be utilized when possible in data analysis. Study coordinators at both sites, will be involved in **recruiting** subjects and obtaining **informed consent** for Aims 1 and 2 of the study. For Aim 1, study coordinators at both sites will **administer the interviews** with patients and providers. For Aim 2, the study coordinators at VAPAHCS and SFVAMC will **administer** the web-based BAI to Veterans randomized to the treatment condition at baseline, along with the assessment survey to all Veteran participants at baseline (in-person interview), and 3- and 6-months post-treatment (phone interview). **Data analysis** will be performed by the PI and Co-Is, and supported by the consultants and research staff as detailed below.

[name]., Principal Investigator

[name] will oversee all aspects of the proposed project in partnership with our partners, The VA Office of Mental Health Services, Office of Mental Health Operations (10N), and VA Office of Public Health. He will supervise study personnel; coordinate data collection protocols, staff training, develop study procedures; and take responsibility for data analysis and the dissemination of findings. He will also co-lead development of the qualitative interviews and protocol, and participate in conducting interviews with staff and patients. He will ensure that the study protocol and all human subjects and data security regulations are followed. Dr.

[name] will also be responsible for communicating and supporting our partners in interpreting the policy and health care implications of our study findings.

[name].; Co-Principal Investigator – not VA Palo Alto

